### **Outcome of the Event:**

- Recovered/resolved
- Recovering/resolving
- Not recovered/not resolved
- Fatal

### **Action Taken with Regard to the Event**

- None
- Study drug dose decreased
- Study drug withdrawn
- Subject Temporarily/permanently discontinued from study

#### *7.1.1.2 Recording Adverse Events*

**Period: Subject Screening to the First Administration of Study Drug:** Non-treatment emergent AEs will be recorded from the time when the subject is screened into the study (date of signature of the informed consent) until first administration of study drug.

**Period: First Administration of Study Drug to Subject's Last Study Visit:** Thereafter all AEs are TEAEs (see Definitions, [Section 7.1.1.1](#)) and will be recorded until the end of study visit has been performed.

**Period After Last Study Visit:** Any SAE occurring after the subject's last study visit that the investigator becomes aware of but considered to be related to the study drug will be reported to the sponsor.

If an AE (serious or not) started during the study but did not end before the final follow-up visit, the investigator should make a reasonable effort to establish the outcome and the end date. If this is not possible, the outcome recorded at the final follow-up visit will be assumed to be the final outcome.

If an event stops and later restarts, all the occurrences must be reported. Adverse events assessed as related to study medication by the investigator and all SAEs must be followed up until resolution.

Signs/symptoms should be documented if a definite diagnosis cannot be established. The investigator should attempt to establish a diagnosis of the event based on signs, symptoms and/or other clinical information. In such cases, the diagnosis should be documented as the AE and/or SAE and not the individual signs/symptoms. If a diagnosis is accompanied by unusual symptoms, the diagnosis itself and the symptoms have to be reported separately.

#### *7.1.1.3 Responsibilities of the Investigator*

Adverse event data should be obtained through observation of the subject, from any information volunteered by the subject or caregiver, or through subject or caregiver questioning. The general type of question asked could be similar to: "Do you have any health problems?" or "Have you had any health problems since your last clinic visit?"

Adverse events are to be documented/recorded accurately and completely on the AE pages of the respective eCRF and in the subject's source data.

All non-treatment and treatment-emergent AEs will be recorded.

This is true even if the study drug was not administered according to the study protocol.

For conditions leading to unplanned surgical procedures the underlying condition, should be documented as an AE, but not the procedure.

#### **Reporting SAEs:**

For AEs that are "serious" (SAEs) additional separate documentation is required using the electronic SAE Forms.

The following variables will be recorded on the electronic SAE Form and on the eCRFs provided in accordance to the eCRF completion guidelines:

- Description of the event, including its duration (date of onset and resolution),
- Whether the event constitutes a SAE or not (if yes, see event seriousness criteria in [Section 7.1.1.1](#))
- Any action taken (e.g., changes to study treatment, other treatment given and follow up tests)
- Outcome of the event
- Investigator's assessment of causality (the relationship to the study treatment[s] and study procedures)
- Severity

For all SAEs where important or relevant information is missing, active follow-up should be undertaken.

The assumption of a causal relationship between the study drug/study conduct and the AE is irrelevant to the obligation to record AEs and notifying AEs to the Sponsor.

**For withdrawals due to AEs** the eCRF page "Study completion / Study termination Form" and a copy of the eCRF AE page needs to be completed and forwarded to [REDACTED]'s Drug Safety Department.

**Overdose** needs to be reported to [REDACTED]'s Drug Safety Department following the criteria for SAE reporting. For this study miglustat overdose is defined as > 800 mg/d.

If additional information is required by the [REDACTED]'s Drug Safety Department, then as a representative of the Sponsor/Pharm-Olam must be granted access to the medical records.

#### *7.1.1.4 Notifying of Serious Adverse Events*

In the event of an SAE, the investigator must inform the [REDACTED]'s Drug Safety department via e-mail or fax using the SAE report/ eCRF page within 24 hours of the study site being informed of the event. At a later date, the [REDACTED] Safety Contact will report to the Sponsor, the Clinical Study Manager, and the Principal Investigator.

##### Adverse Event Reporting Contact:

Pharm-Olam Drug Safety

E-mail: [REDACTED]

For questions regarding SAEs, or to provide information that cannot be provided electronically, or to notify the Sponsor of an SAE in the event of technical failure, the investigator should contact Pharm Olam's Drug Safety Department. Contact information will be provided in a separate document.

Investigators or other site personnel should inform [REDACTED]'s Drug Safety department of any follow-up information that becomes available for a previously reported SAE immediately but no later than 24 hours of becoming aware of the information. Follow-up reports (as many as required) should be completed and faxed or e-mailed following the same procedure above. Any requested supporting documentation (e.g., ECG, laboratory results, autopsy report) should be sent to the [REDACTED]'s Drug Safety department.

Prior to forwarding any personal data for safety reporting, the documents need to be coded in a way that keeps the subject's identity confidential (e.g., by using the subject's identification code, randomization number, etc.).

For fatal and life-threatening SAEs, [REDACTED]'s Drug Safety department will work with the investigator to ensure that any additional information is provided by the investigator within 1 business day. The investigator will ensure that all the necessary information for all other SAEs will be provided within the timelines stipulated by the Sponsor when the request for information is made.

If required, the investigator is responsible for informing local Institutional Review Boards (IRBs) of safety reports in compliance with applicable regulatory requirements. Copies of all correspondence relating to reporting of any safety reports to the IRB should be maintained in the Investigator Site File (ISF) / Regulatory Binder.

The Sponsor's representative is responsible for fulfilling all obligations regarding notification of Regulatory Authorities and IRBs according to applicable regulatory requirements (expedited and periodic reporting, e.g., serious unexpected suspected adverse reactions, Development Safety

Update Report). In addition, the Sponsor will provide safety information to investigators according to the current regulations.

#### *7.1.1.5 Laboratory Values*

Laboratory values are also defined as AEs if they are outside the normal and if, in the opinion of the investigator, they represent a clinically relevant change versus pre-treatment values.

If abnormal laboratory values are signs of an AE (e.g., an infection) that has already been recorded, the respective abnormal laboratory value does not constitute a separate AE.

Wherever reasonable the reporting investigator will use the clinical term rather than the laboratory term (e.g., anemia versus low hemoglobin value).

#### *7.1.2 Pregnancy*

Occurrence of pregnancy in a subject during a clinical study must be recorded.

Each pregnancy that starts during the study must be reported by the investigator to [REDACTED]'s Drug Safety department within 24 hours of the investigator's knowledge of the pregnancy by using the Pregnancy Reporting Form. Study treatment should be stopped immediately after being aware of the event. Any adverse outcome of the pregnancy must be recorded and notified on the "Drug Exposure via Parent Report Form" or SAE Form if this meets SAE reporting criteria. The investigator should make any reasonable effort to follow any pregnancy until birth of the child.

Blood test at baseline then urine test is acceptable.

#### *7.1.3 Laboratory Parameters*

Laboratory assessments will be performed by a central laboratory. The tests listed in [Table 7-1](#) will be conducted on samples collected and analyzed by standard laboratory procedures at the time points designated on the Schedules of Activities ([Section 1.3](#)). Tests that are not done must be reported as such on the eCRFs. The total volume of blood drawn per patient for the entire duration of the study is planned to be approximately 440 ml.

**Table 7-1 Laboratory Parameters**

Hematology		
Hemoglobin	Leukocytes	
Biochemistry		
Creatinine Total bilirubin (direct and indirect if values were above normal ranges) HbA1C	Alkaline phosphatase Aspartate aminotransferase Alanine aminotransferase Gamma glutamyl transpeptidase Creatine kinase	Sodium Potassium Cholesterol (total, HDL, LDL) Triglycerides

Urine		
Glucose Nitrate pH	Hemoglobin Leukocytes Specific gravity	Protein Ketones
Other Tests		
HIV A	Hepatitis B A	Hepatitis C A
Pregnancy test in women of childbearing potential		

HbA1c=hemoglobin A1c; HDL=high-density lipoprotein; LDL=low-density lipoprotein

A Only if there is no medical history of these diseases or no previous testing.

#### **7.1.4 Vital Signs**

Vital signs will be measured before any IP intake and recorded at the time points designated on the Schedules of Activities ([Section 1.3](#)). The following measurements must be performed: systolic/diastolic blood pressure and heart rate. Vital signs will be measured after the subject has been in the sitting position for at least 5 minutes. All measurements will be recorded on the vital signs eCRF. Abnormal test results may be repeated at the discretion of the investigator and must be reported on the corresponding eCRF. When vital signs, ECGs, and/or blood sample collection occur at the same time, vital signs should be performed before ECGs and/or blood sample collection.

#### **7.1.5 Electrocardiograms**

During the study, 12-lead ECGs will be performed at the time points designated on the Schedules of Activities ([Section 1.3](#)).

The subject must be in a supine position in a rested and calm state for at least 5 minutes before ECG assessment is conducted. If the subject is unable to be in the supine position, the subject should be in the most recumbent position possible. All ECGs should be performed in a standardized method, in triplicate, and approximately 30 seconds apart, prior to blood draws or other invasive procedures. Each ECG must include the following measurements: QRS, QT, corrected QT, RR, and PR intervals.

A designated cardiologist will review and sign all ECGs. Results must be summarized in writing and classified as normal; abnormal; abnormal, clinically relevant; or abnormal, not clinically relevant. Once signed, the original ECG tracing will be retained with the subject's source documents. At the request of the Sponsor, a copy of the original ECG will be made available.

#### **7.1.6 Physical Examination**

The investigator or qualified designee will perform a physical examination (genitourinary examination not required) at screening and baseline and at the time points designated on the Schedules of Activities ([Section 1.3](#)). Pre-dose abnormal findings will be reported on the medical history eCRF. Any adverse change from the baseline physical examination will be documented on the AE eCRF.

A physical examination will include inspection of general appearance, skin, neck (including thyroid), eyes, ears, nose, throat, heart, lungs, abdomen, lymph nodes, extremities, musculoskeletal system, and nervous system.

An abbreviated physical examination will assess only the general appearance of the patient and is only required when a complete exam is not indicated.

A standardized neurological exam will be performed by a pediatric neurologist or qualified individual. The neurological exam will take into account potential visual impairment. The evaluation will include, but is not limited to mental status, cranial nerves, motor function, and sensory and cerebellar functions.

### ***7.1.7 Additional Safety Assessments***

Slit-lamp evaluation will be performed during ophthalmic efficacy assessment to monitor ocular cataracts and ocular opacity.

### ***7.1.8 Unanticipated problems***

#### **Definition**

Any incident, experience, or outcome that meets **all** the following criteria:

- Unexpected in terms of nature, severity, or frequency given (a) the research procedures that are described in the protocol-related documents, such as the Institutional Review Board (IRB)-approved research protocol and informed consent document; and (b) the characteristics of the participant population being studied; **and**
- Related or possibly related to participation in the research (“possibly related” means there is a reasonable possibility that the incident, experience, or outcome may have been caused by the procedures involved in the research); **and**
- Suggests that the research places participants or others (which may include research staff, family members or other individuals not directly participating in the research) at a greater risk of harm (including physical, psychological, economic, or social harm) than was previously known or expected.

#### **Unanticipated problems reporting**

See Section 7.1.1.3 Responsibilities of the Investigator

## **7.2 Other Parameters**

Blood samples for analysis of miglustat will be taken at first dose (Week 1) and at end of titration.

The following windows pertain to the PK draw times:

Scheduled PK Draw Time	Allowed Window
Pre-dose (0) to 3 hours	± 5 minutes
4 hours–8 hours	± 30 minutes
24 hours	± 2 hours

Blood draws will occur at the following time points.

- Week 1: pre-miglustat dose (0), 1, 2, 2.5, 3, 4, 6, 8, and 24 hours. Confinement between the 8- and 24-hour time points is not necessary. Subjects may return to the Local Health Center / stay at Subject's Home the following day with a window of  $24 \pm 2$  hours. The 24-hour time point must be done before the Day 2 dose of miglustat is taken.
- Week 9: pre-miglustat dose (0), 1, 2, 2.5, 3, 4, 6, and 8 hours. Subsequent daily miglustat dose(s) (if applicable) will be administered after the 8-hour blood draw has been performed.

### 7.3 Efficacy Assessments

Efficacy assessments (UBDRS; seizure frequency (diary); Vineland-3; visual acuity, visual field (if feasible) , and retinal thickness using OCT; volumetric assessments using MRI; CSF, blood and urine biomarkers for neurodegeneration) will be conducted at the time points outlined on the Schedules of Assessments ([Section 1.3](#)).

#### 7.3.1 Unified Batten Disease Rating Scale

The UBDRS is a scale specifically developed to assess symptoms in CLN3 subjects ([Marshall 2005 et al., Kwon et al., 2011, Cialone et al., 2012., Masten et al., 2020](#)). The UBDRS consists of 7 different domains: (1) physical, (2) seizure, (3) behavioral, (4) capability normal vision (will not be assessed) (5) capability actual vision, (6) NCL history and (7) clinical summary including 7 global impression scales (Appendix 2). The physical domain consists of 20 different items based on a neurological assessment; higher scores indicate more severe disease. The seizure domain consists of 12 different assessments based on parent/caregiver information: frequency of seizure types (8 items), medical consequences of seizures (4 items), higher scores indicate more severe disease. The behavior domain consists of 10 different assessments based on parent/caregiver information; higher scores indicate more severe disease. The capability domain has 5 different assessments based on parent/caregiver information; lower scores indicate more severe disease, and NCL history including 8 items to document the onset of typical symptoms. The UBDRS assessments via live video -interview will be performed at the time points outlined on the Schedules of Assessments, if video interview is not possible for technical reasons, patients will be assessed at the NIH by a UBDRS trained rater. In cases of any event precluding safe travel by participants to NIH, the assessment will be performed remotely according to instructions delivered by Rochester University ([Section 1.3](#)). A copy of the UBDRS is provided in [Section 13.2](#) . In case of sedation for other examinations (e.g. MRI, OCT, lumbar puncture), UBDRS will be performed either before or  $> 24$  hours after sedation.

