	Visit 1 Assessments at TCH (Screening and Baseline Safety)	Screening confirmation by TCH A (Phone Visit)	Visit 2 Assessments at NIH CC B and final enrollment (Baseline Efficacy Assessments)	Treatment start Local Health Center/ Subject's Home	Visit 3 NIH CC B	Visit 4 NIH CC B	Visit 5 NIH CC B	Visit 6 Early termination TCH B
				Day 1 Week 1 Up to 14 days between V2 and first dose	Week 26 ( $\pm$ 1 month)	Week 52 ( $\pm$ 1 month)	Week 78 ( $\pm$ 1 month)	Early Access Program start
Days -42 to -1								
MRI K			X		X			
Seizure diary dispensation L	X							
Blood for biomarkers			X		X	X		
Spot urine for biomarkers			X		X			
Lumbar puncture for CSF collection (biomarkers) K			X		X			

A After TCH PI determination of subject eligibility, study staff will inform the subject and will schedule NIH CC baseline visit.

B In cases of any event precluding safe travel by participants to NIH (i) for inclusion visit: beyond 1.5 months, the safety labs will be repeated at NIH. However, the total duration between the 2 inclusion visits should not exceed 3 months. Time between NIH visit and first drug administration should be also maintained within a reasonable timeframe (1 month). (ii) during the course of the study: evaluations will be performed (1) at the Local Health Center / Subject's Home for: labs, ECG (if feasible), physical exam, vital signs, weight, adverse events, or (2) via remote methods for : history, UBDRS, Vineland-3, adverse events, concomitant meds, seizure diary or (3) could be deferred (+/- 1 month) for: neurological exam, ophthalmology exam, MRI, lumbar puncture.

C Vital signs include systolic and diastolic blood pressure [sitting for 5 minutes] and pulse rate.

D A standardized neurological exam will be performed by a pediatric neurologist or qualified individual. The neurological exam will take into account potential visual impairment. The evaluation will include, but is not limited to mental status, cranial nerves, motor function, and sensory and cerebellar functions.

E The subject must be in supine position in a rested and calm state for at least 5 minutes before ECG assessment is conducted. Electrocardiograms should be performed in a standardized method, in triplicate, and approximately 30 seconds apart, prior to blood draws or other invasive procedures. Each ECG must include the following measurements: QRS, QT, QTc, RR, and PR intervals.

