F Since last Local Health Center/ Subject's Home visit.

G Chemistry laboratory parameters include HbA1c, creatinine, total bilirubin (direct and indirect if values were above normal ranges), alkaline phosphatase, aspartate aminotransferase, alanine aminotransferase, gamma glutamyl transpeptidase, creatine kinase, sodium, potassium, cholesterol, and triglycerides. Hematology laboratory parameters include hemoglobin, hematocrit, erythrocytes, thrombocytes, and white blood cell count with differential (for an absolute neutrophil count, lymphocyte count and monocyte count). Dipstick urinalysis includes glucose, nitrate, hemoglobin, leukocytes, protein, pH, ketones, and specific gravity.

H All subjects will be assayed for anti-hepatitis C antibody, hepatitis B surface antigen, and human immunodeficiency virus.

I Assessment will be done either before or > 24 hours after sedation. All domains are administered at baseline. If video interview is not possible for technical reasons, patients will be assessed at the NIH by a UBDRS trained rater. In cases of any event precluding safe travel by participants to NIH, the assessment will be performed remotely according to instructions delivered by URMC

J Assessment will be done either before or > 24 hours after sedation. The Communication, Daily Living Skills, Socialization and Motor Skills domains are assessed.

K Subjects who cannot cooperate with the MRI study, ophthalmology exam, or lumbar puncture procedure may be sedated. Baseline OCT will be obtained in all study participants. In those participants with no light perception vision, dense cataracts, or other ophthalmologic findings that produce significant artifacts in the OCT images, OCT imaging will not be repeated.

L A seizure diary will be completed on a daily basis, beginning at screening. The baseline seizure frequency will be calculated based on data collected from screening to first dose of study drug.

**Table 1-3 Miglustat Dose-titration and Pharmacokinetic Sampling Period – Local Health Center or Subject’s Home (Weeks 1 Through 9)**

	Day 1 – Week 1 (Within 42 days of screening)	Dose-titration Period							
		Day 8±2 Week 2	Day 15±2 Week 3	Day 22±2 Week 4	Day 29±2 Week 5	Day 36±2 Week 6	Day 43±2 Week 7	Day 50±2 Week 8	Day 57±2 Week 9
General Assessments									
Abbreviated physical examination A	X				X				X
Vital signs B	X	X	X	X	X	X	X	X	X
Weight	X	X	X	X	X	X	X	X	X
Concomitant medications	X	X	X	X	X	X	X	X	X

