##### 4. PASSIVE MOTION-ARMS

Right  Left   
4a.  4b.

0 = normal tone/full range  
1 = mildly increased tone/full range  
2 = moderately increased tone/full range  
3 = markedly increased tone/incomplete range  
4 = minimal or no passive range of motion

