**Table 2. UBDRS Domains/Subscales and Analysis Methods**

Domain	Contributing Questions	Method of Summarization	Imputation Rules
Physical Assessment	1, 1A, 2, 3, 4A, 4B, 5A, 5B, 6, 7A, 7B, 8A, 8B, 9A, 9B, 10A, 10B, 11, 12, 13, 14A, 14B, 15, 16, 17, 18, 19, 20	Sum of scores of individual questions divided by number of questions (28).	Missing or not done individual question values will be imputed with the worst possible value (i.e., 4) for summaries
Modified Physical Assessment Subscale	1, 1A, 3, 4A, 4B, 5A, 5B, 6, 9A, 9B, 11, 12, 13, 14A, 14B, 19	Sum of scores of individual questions divided by number of questions (16).	As for Physical Assessment domain
Physical Assessment 5-item Subscale	1, 11, 12, 13, 19	Sum of scores of individual questions divided by number of questions (5).	As for Physical Assessment domain
Physical Assessment 2-item Subscale	1, 12	Sum of scores of individual questions divided by number of questions (2).	As for Physical Assessment domain
Seizure Assessment	23-34	Sum of scores of individual questions divided by number of questions (12).	Missing or not done individual question values will be imputed with the worst possible value for summaries: 1. Questions 23, 25, 26, 27, 29 – 6, 2. Questions 24, 28, 30 – 5, 3. Questions 31, 32 – 3. 4. Question 33 – 2, 5. Question 34 – 1.
Behavioral Assessment (Past Month)	36A, 36B, 37A, 37B, 38A, 38B, 39A, 39B, 40A, 40B, 41A, 41B, 42A, 42B, 43A, 43B, 44A, 44B, 45	Sum of scores of individual questions divided by number of questions (19).	Missing or not done individual question values will be imputed with the worst possible value for summaries: 1. Question 45 – 1, 2. All other questions – 3.
Capability Assessment Given Actual Vision	52-56	Sum of scores of individual questions divided by number of questions (5).	Missing or not done individual question values will be imputed with the worst possible value for summaries: 1. Questions 52-55 – 3, 2. Question 53 – 2.
Clinical Summary	61-67	Each question (including 6 CGIs*** and one assessment of change) will be presented separately.	Missing or not done individual question values will be imputed with the worst possible value for summaries (5).  Question 61 (Assessor's global impression of change since last assessment) value "Not applicable (never seen before)" will not be imputed.

\* NCL history domain of UBDRS (completed by first rater) will be summarized with baseline disease history data

(see details in section [5.7](#)).

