\*\* Capability assessment assuming normal vision is not assessed in this study.

\*\*\* CGI = Clinician Global Impression.

Domain scores, subscale scores and individual question scores (only for Clinical Summary domain which does not have domain score), and their respective changes from baseline will be summarized at each scheduled post-baseline visit. Baseline will be defined as last value collected before first study drug administration; both data collected at scheduled and unscheduled visits will be included in baseline derivation. For Clinical Summary domain question 61 (Assessor's global impression of change since last assessment), only observed values (not change from baseline) are presented.

UBDRS data (including both individual and domain scores) will be listed.

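### UBDRS change from baseline takes no account of rating mode or rater, although about 6 to 10 of the 28 physical items appear to need an examiner's hands and items not done are scored as worst

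*Protocol*

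**What the plan says.** **Rating mode.** Protocol 7.3.1 sets the default: "The UBDRS assessments via live video -interview will be performed at the time points outlined on the Schedules of Assessments". There are two contingencies. The first is that "if video interview is not possible for technical reasons, patients will be assessed at the NIH by a UBDRS trained rater". The second applies when a subject cannot travel safely to NIH: "the assessment will be performed remotely according to instructions delivered by Rochester University". Footnote I of Table 1-2 repeats the travel rule. Footnote B lists what may be done "via remote methods for : history, UBDRS, Vineland-3, adverse events, concomitant meds, seizure diary". In the same circumstances, footnote B and Protocol 4.1 defer the neurological examination by up to a month. Protocol 4.1 confines the travel exception to the period after the baseline visit.

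No passage asks that a subject keep the same mode or rater. None says who tests tone, power or balance when the rater is on a screen.

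**Form.** Appendix 2 has examiner codes (items 22, 35, 46, 57 and 68) but no field for mode. An item that cannot be rated is entered as U.

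**Analysis.** SAP Table 2 scores the physical domain as the sum over 28 questions divided by 28. Missing or not-done questions are set to 4. SAP 5.2.1 then takes the domain and subscale scores, and "their respective changes from baseline will be summarized at each scheduled post-baseline visit". Mode and rater do not appear in the SAP.

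**The concern.** A change score is interpretable only if both visits measure the same thing in the same way. The physical domain rests on a neurological assessment (Protocol 7.3.1). Some of its items grade what an examiner feels or provokes: resistance to passive movement, strength against resistance, recovery from a backward pull. When travel is unsafe, the protocol postpones the neurological examination but sends the UBDRS to remote methods.

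Two routes to an artefact follow. A different mode or rater may grade the same sign differently. An item that cannot be examined may be entered as U and then, if U counts as missing or not done, become a 4 by rule.

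The UBDRS carries much of the efficacy description. It defines the Efficacy Population (SAP 4). Vineland-3, MRI and biomarkers are only listed in this SAP. Apart from intraocular pressure, the UBDRS is the only efficacy measure summarized as change from baseline. With about six subjects and no control arm, one affected subject is visible in the mean.

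**Working it through.** **Inputs.** Item lists, denominators and the imputed value 4 come from SAP Table 2. Anchors, graded 0 to 4, come from Protocol Appendix 2. The six subjects come from Protocol 8.10 and SAP 2.2. The assumptions are the contact set in step 2, one subject switching, all contact items affected, U handled as missing or not done, and a common true item score *t* from 0 to 3.

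**1. Reproduce the denominator.** Appendix 2 has 20 numbered physical items, plus item 1A, plus a second side for items 4, 5, 7, 8, 9, 10 and 14: 20 + 1 + 7 = 28. This agrees with SAP Table 2.

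**2. Count contact items.** Passive motion (4a, 4b, 5a, 5b, 6) gives 5, and the pull test (13) gives 1, so 6. Power (7a, 7b, 8a, 8b) adds 4, making 10. Power is arguable: some of its anchors refer to resistance, others to drift or gravity, which can be watched.

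| Score | Items *m* | Contact items *k* (power counted) | *k* (power not counted) |
|---|---|---|---|
| Physical domain | 28 | 10 (36%) | 6 (21%) |
| Modified subscale | 16 | 6 (38%) | 6 (38%) |
| 5-item subscale | 5 | 1 (20%) | 1 (20%) |
| 2-item subscale | 2 | 0 | 0 |

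Power is not in the modified, 5-item or 2-item lists, so its classification matters only for the full domain.

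**3. Contact items not done at one visit and imputed as 4.** Subject shift = *k*(4 − *t*)/*m*. Shift in the six-subject mean = that value divided by 6. For example, with *k* = 10 and *t* = 0: 10 × 4/28 = 1.43, and 1.43/6 = 0.24.

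| Score | Subject shift, *t* = 0, 1, 2, 3 | Mean shift, *t* = 0, 1, 2, 3 |
|---|---|---|
| Physical, *k* = 10 | 1.43, 1.07, 0.71, 0.36 | 0.24, 0.18, 0.12, 0.06 |
| Physical, *k* = 6 | 0.86, 0.64, 0.43, 0.21 | 0.14, 0.11, 0.07, 0.04 |
| Modified, *k* = 6 | 1.50, 1.13, 0.75, 0.38 | 0.25, 0.19, 0.13, 0.06 |
| 5-item, *k* = 1 | 0.80, 0.60, 0.40, 0.20 | 0.13, 0.10, 0.07, 0.03 |

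**4. No imputation; each contact item graded one point differently (assumption).** Subject shift = *k*/*m*: 10/28 = 0.36, or 6/28 = 0.21. Mean shift: 0.36/6 = 0.06, or 0.21/6 = 0.04.

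**5. Direction.** Under step 3 the artefact looks like worsening when the unexamined visit is the follow-up. It looks like benefit when it is the baseline. Off-site remote rating is excluded at baseline, but baseline by video followed by in-person rating is possible.

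**The case against.** - **The modes differ less than a count of three suggests.** The default and the travel fallback are both remote, and in-person rating needs a technical failure and a trained rater. This stands: the main contrast is remote versus in person, and both departures from the default are contingencies whose frequency the documents do not give.
- **On-site help is possible.** At default visits the subject is at NIH while rated by video, so staff there may perform the manoeuvres. If they do, video and in-person ratings need not differ on these items. If nobody does, the items may be unrated at baseline too, and 4 minus 4 gives no shift. This is a fair limit, but the documents do not settle which holds. It also leaves open a switch from an assisted visit to one off site.
- **The contact set is a judgement.** The form does not label items this way. This stands, hence the range of 6 to 10. The point concerns the physical domain; seizure, behavior and capability ratings rely on caregivers.
- **Nothing formal depends on it.** Efficacy is secondary and descriptive, with no test or decision rule. Item scores are listed, and with six subjects they can be inspected. This limits the weight. However, listings that are not required to show mode would not tell a reader which changes to distrust.

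A reader might infer that subjects may be rated from home at any visit. The documents do not support this: home is not named as a UBDRS setting, and Protocol 4.1 applies the travel exception only after baseline. A reader might also infer that the 2-item speech-and-gait subscale is immune to mode. It contains no contact items, but nothing shows that speech or gait is graded alike on video and in person.

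**Conclusion.** The concern holds in a limited form. The protocol permits a change of mode or rater within a subject. The SAP neither records nor considers it, and its worst-score rule can turn items left unexamined because of the mode into apparent change. In the case worked here, one subject's physical score moves by 1.43 to 0.36 on a 0-to-4 scale, and the six-subject mean by 0.24 to 0.06. With only 6 contact items the ranges are 0.86 to 0.21 and 0.14 to 0.04. Without imputation, an assumed one-grade difference on 10 items gives 0.36 and 0.06.

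These figures rest on the inferred contact set, on every such item being affected at one visit only, and on U being treated as missing or not done. They show what the rules allow, not what happened. A reader might infer that observed UBDRS change in this trial is an artefact, or can never be separated from disease change. The documents support neither: switch frequency is unknown, and item scores and examiner codes offer a partial check. The change is worth making before the SAP is final because it is cheap and concerns the main summarized clinical scale.

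**What to change.** In SAP 5.2.1:

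1. List the rating mode and examiner code with every UBDRS score. Take mode from source records if it is not on the CRF.
2. Flag each visit whose mode or examiner differs from that subject's baseline.
3. Add a supportive summary of physical-domain change restricted to pairs of visits rated in the same mode.
4. As sensitivity only, show physical change on the items actually rated at both visits, without worst-score imputation for items that could not be examined because of the mode. State how a U entry is handled.
5. Keep the 28-item score as the main summary. Note that the 2-item subscale contains no contact items, without calling it robust to mode.

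For any visits still to come, Protocol 7.3.1 should ask for the baseline mode and rater where feasible.

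The cost is one data field, possibly filled retrospectively, some SAP wording and one supportive table. The sensitivity summaries will rest on fewer subjects or fewer items and should be read as such.
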